5.4 Packaging, Labeling and Storage

#### 5.4.1 Packaging and Labeling

Packaging and labeling of Fidmi Feeding device (study Investigational Medicinal Product) will be performed in compliance with relevant regulatory requirements of GMP guidelines.

Further details are elaborated in the Investigational Brochure.

In order to be delivered ready for use each 'Patient Pack' are assembled with:

- 1X Measurement pack (Fidmi Medical Stoma Measuring Device), packed in a heat sealable EtO compatible sterilization pouch
- 1X Placement and Feeding pack (Fidmi Medical Enteral Feeding Device), sealed in a rigid tray PET-G blister pack with a Tyvek® lid (heat pressed)
- 5X Disposable Tube Pack (Replaceable Tube Pack), sealed within a rigid tray blister pack with a Tyvek® lid
- 10X Extension tubes.

Packs are plug-sealed and packed in adhesive-sealable wrap packaging pouches/blister pack. These are sealed and labeled with the patient details and expiry time. Device packs are transferred to the site for the clinical usage according to the study protocol.

#### Illustration samples of Device Package Labels:

[figure not shown]
Fichmedical
Fidmi Medical Stoma Measuring Device,
Version: UDI : CT
Sponsor: Fidmi Medical Ltd., [name]
For clinical trial use only
Instruction for Use and Warnings are enclosed inside the kit
0297-17-SZMC Shaare Zedek Medical Center, [name]
[name].
Trial subject ID
Storage conditions: Temperature: - 30º C – (+60º C), Humidity: ≤
90%, Do not store device in direct sunlight
Keep out of reach of children

		Protocol No.: FM-01
medical	– Study Protocol –	Version 5.1
	- Study Protocor –	Page 19 of 55
Safety and Usability Evaluation of the Fidmi Low-Profile		CONFIDENTIAL

**F**edreal

**Enteral Feeding Device** 

Fidmi Medical Enteral Feeding Device, Version: \_\_\_\_\_ UDI : CT...\_ Sponsor: Fidmi Medical Ltd., [name] For clinical trial use only Instruction for Use and Warnings are enclosed inside the kit 0297-17-SZMC Shaare Zedek Medical Center, [name]. Trial subject ID \_\_\_\_\_ Storage conditions: Temperature: - 30° C – (+60° C), Humidity: ≤ 90%, Do not store device in direct sunlight Keep out of reach of children

		Protocol No.: FM-01
- Study Protocol -	Version 5.1	
	- Study Protocol -	Page 20 of 55

CONFIDENTIAL

Safety and Usability Evaluation of the Fidmi Low-Profile Enteral Feeding Device

תנאי אבסון: טמפ' (C º60+) – C º00 - לחות <90%, אין להניח תחת שמש ישירה להרחיק מהישג ידם של ילדים

ficmi
פידמי מכשיר הזנה תוך בטנית
גרסה:מספר מזהה
היזם: פידמי מדיקל בע"מ, [name]
לשימוש בניסוי רפואי בלבד
הוראות שימוש ואזהרות למשתמש מצורפים בערכה
SZMC-0297-17. , מרכז רפואי שערי צדק, ד"ר [name]
מספר נבדק
תנאי אבסון: טמפ' (C – (+60º C) - 30º C – לחות <90%, אין להניח תחת שמש
ישירה
להרחיק מהישג ידם של ילדים

ערכת צינוריות החלפה גרסה:\_\_\_\_\_\_מספר מזהה\_\_\_\_\_ היזם: פידמי מדיקל בע"מ, [name] לשימוש בניסוי רפואי בלבד הוראות שימוש ואזהרות למשתמש מצורפים בערכה הוראות שימוש ואזהרות למשתמש מצורפים בערכה SZMC-0297-17 , מרכז רפואי שערי צדק, ד"ר [name] SZMC-0297-17 , מרכז רפואי שערי צדק, ד"ר [name] הוראות אבסון: טמפ' (C י100+) – 2 י00 - לחות <90%, אין להניח תחת שמש ישירה להרחיק מהישג ידם של ילדים

#### 5.4.2 Transport and Storage

- Temperature:  $-30^{\circ} \text{ C} (+60^{\circ} \text{ C})$ , Humidity:  $\leq 90\%$
- Do not store Fidmi Feeding device and Replacement Tubes in direct sunlight
- Place the Disposable Tubes in their box or in a safe, dry, cool place.
- 6 Potential Risks and Benefits

#### 6.1 Known Potential Risks

Complications from PEG tube placement can be classified as major or minor (8):

ficmedical	– Study Protocol –	Protocol No.: FM-01 Version 5.1 Page 21 of 55
Safety and Usability Evaluation Enteral Feeding Device	of the Fidmi Low-Profile	CONFIDENTIAL

Minor complications include:

- i. Wound infection,
- ii. Peristomal leakage,
- iii. Wound leakage,
- Wound bleeding, iv.
- ٧. Hemorrhage bleeding
- Cutaneous or gastric ulceration, vi.
- vii. Pneumoperitoneum,
- viii. Temporary ileus,
- ix. Aspiration
- Gastric outlet obstruction. х.
- xi. Clogging
- xii. Tube dysfunction

Major complications include:

- i. Necrotizing fasciitis,
- ii. Esophageal perforation,
- iii. Gastric perforation,
- iv. Colocutaneous fistula,
- Buried bumper syndrome, ٧.
- Inadvertent PEG removal. vi.
- vii. Small bowel obstruction
- viii. Hepatic injury

#### 6.2 Known Potential Benefits

Fidmi Device will provide simple initial insertion, home replacement and removal procedures and would contribute to improved life quality of the patient.

Fidmi Device is the first presented "low-profile device from day 1", easily hidden under clothing and not limiting mobility.

Fidmi Device overcomes most of the currently suffered shortcomings. Fidmi device can ensure less complications, less follow-up visits, 5 minute replacement, 2 year lifetime.

fich medical	– Study Protocol –	Protocol No.: FM-01 Version 5.1 Page 22 of 55
Safety and Usability Evaluation Enteral Feeding Device	of the Fidmi Low-Profile	CONFIDENTIAL

#### 7 TRIAL OBJECTIVE AND HYPOTHESIS

#### 7.1 STUDY OBJECTIVES

To evaluate the safety and effectiveness of the: insertion, long term utilization, dismantling and removal, as a treatment for adult patients with a need for enteral feeding (Percutaneous Endoscopic Gastrostomy).

#### 7.2 HYPOTHESIS

Insertion of Fidmi PEG device will reduce complication rate, reduce tedious patient follow up visits at the hospitals and significantly shorten the time of replacement from currently 45 minutes (in average) to 5 minutes. Above all, Fidmi device lifetime will offer 2 years' time instead of the current 3-6 months.

#### 7.3 STUDY PARTICIPATION DURATION

overall, under the study protocol, each patient enrolled into the study will undergo a total of 7 visits including 4 follow-up visits during study duration of 120 days±14 days.

#### 7.4 STUDY DURATION

15 patients will be enrolled to the study. We expect enrollment to occur over a 8month period and the data analysis period of time will be 1 month time.

fich medical	– Study Protocol –	Protocol No.: FM-01 Version 5.1 Page 23 of 55
Safety and Usability Evaluation of the Fidmi Low-Profile Enteral Feeding Device		CONFIDENTIAL

#### 8 TRIAL DESIGN

#### 8.1 STUDY DESIGN

The Fidmi trial is an early feasibility Open Label single center study consists of Single Group Assignment, to evaluate the safety and preliminary efficacy of Fidmi Low-Profile Enteral Feeding Device as a treatment for adult patients with a need for enteral feeding (Percutaneous Endoscopic Gastrostomy placement).

#### 8.2 STUDY ENDPOINTS

#### Safety Endpoints:

- 1. Evaluate incidence of adverse events according to National Cancer Institute (NCI) Terminology Criteria for AE v4.0 common terminology criteria for AE. (CTCAE) during insertion, patient utilization or removal of Fidmi PEG device.
- 2. Concomitant medications
- 3. Physical examination (of insertion site).
- 4. Unscheduled hospital readmission.

#### **Performance Endpoints:**

#### Primary:

- 5. To evaluate accidental dislodgement during study follow up.
- 6. To evaluate unscheduled replacement rate (only clogged tubes).
- 7. To evaluate patient pain during removal.
- 8. To evaluate of uneventful (flawless) insertion and removal of Fidmi PEG device.
- 9. The ability to provide prescribed (and not partial) enteral feeding throughout the study period.

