#### 3. PROTOCOL SYNOPSIS

Protocol Number	FM-01
Protocol Title	Safety and Usability Evaluation of the Fidmi Low-Profile Enteral Feeding Device
Participating Countries	IL
Study Type	Interventional
Study Design	The Fidmi trial is an early First In Human feasibility Open Label single center study consists of Single Group Assignment, to evaluate the safety and preliminary efficacy of Fidmi Low-Profile Enteral Feeding Device as a treatment for adult patients with a need for enteral feeding (Percutaneous Endoscopic Gastrostomy placement).
Investigational Study Device	Fidmi Feeding Device, by Fidmi Medical Ltd.

ficmedical,	– Study Protocol –	Protocol No.: FM-01 Version 5.1 Page 6 of 55
	6 1 - 1 1 1 1 1	

Safety and Usability Evaluation of the Fidmi Low-Profile Enteral Feeding Device

CONFIDENTIAL

Study Purpose	To evaluate the safety and effectiveness of the Fidmi PEG device: insertion, long term utilization, dismantling and removal		
Study Population	15 adult patients, male or female suffering from dysphagia, who are scheduled for PEG (Newly PEG insertion (minimum 10 patients) and PEG replacement involving endoscopy procedure)		
Study Procedures	15 Consecutive adult patients with need for enteral feeding Scheduled for PEG with protocol sedation. The patients will attend the following: Visit 1: Screening and Enrollment Visit 2: Insertion or replacement in the Endoscopy suite, Visit 3: Follow up after 2 days (sub-investigator visit in patient facility) Visit 4: Follow up after 1 month (sub-investigator visit in patient facility) Visit 5: Follow up after 2 month (phone call) Visit 6: Follow up after 3 months and Fidmi device removal Visit 7: Follow up after 4 months, X-ray and termination		
	
 
Safety Endpoints:
 
Number of Participants With Treatment-Related Adverse Events as Assessed by CTCAE v4.0 through study completion.
 
Number of participants requiring unscheduled hospital readmission related to Fidmi Feeding device through study completion.
 
Performance Endpoints:
 
		
Study Endpoints	
 
Primary:
 
3. Number of accidental dislodgements during study follow up until device removal at 3 months.
 
		
	
 
Number of unscheduled internal tube replacements (only clogged tubes) until device removal at 3 months.
 
		
	
 
Patient Pain on the Visual Analog Scale during device removal at 3 months.
 
		

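### The synopsis and Section 8.2 define the safety and primary performance endpoints differently with neither given precedence, and the Section 11.3 rule on pre-existing conditions is garbled

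*Protocol*

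**What the plan says.** Safety, synopsis (Section 3): two endpoints, "Number of Participants With Treatment-Related Adverse Events as Assessed by CTCAE v4.0 through study completion" and "Number of participants requiring unscheduled hospital readmission related to Fidmi Feeding device through study completion".

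Safety, Section 8.2: four endpoints. These are the incidence of CTCAE v4.0 adverse events "during insertion, patient utilization or removal of Fidmi PEG device"; "Concomitant medications"; physical examination of the insertion site; and unscheduled readmission. Neither the AE item nor the readmission item mentions a relation to the device.

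Primary performance: both lists have accidental dislodgement, unscheduled replacement of clogged tubes, pain at removal, and uneventful insertion and removal. Section 8.2 adds a fifth: "The ability to provide prescribed (and not partial) enteral feeding throughout the study period".

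Procedure time is a secondary endpoint in the synopsis. It is not in the secondary list of Section 8.2 and appears in Section 8.3 only as a usability measure.

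Section 12 plans descriptive statistics and presents AEs by, among other things, seriousness and relation to the product. It names no primary endpoint and refers to neither list.

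On pre-existing conditions, a sentence in Section 11.3 denies them AE status *only if* they become worse than expected.

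**The concern.** This is not a short summary of a fuller list. Each list holds something that the other lacks, and the two differ in what they count. For a first-in-human device study, the number of participants with AEs is the main product. As written, that number may be restricted to related events or not, and may or may not extend to the post-removal month, depending on the section that the reader opens. The same choice of relatedness exists for readmissions. Whether prescribed feeding is a primary result at all is also open. If none of this is settled beforehand, it can be settled after the data are seen.

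The Section 11.3 sentence raises a different problem. The endpoint mismatch concerns which recorded events to report. The sentence concerns whether an event is recorded in the first place.

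**Working it through.** The plan states no power, error rate or sample size calculation (Sections 3 and 8.4), so there is no design figure to reproduce. The check is a comparison of the two lists.

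| | Synopsis (Section 3) | Section 8.2 |
|---|---|---|
| Safety endpoints | items 1–2: 2 | items 1–4: 4 |
| Primary performance | items 3–6: 4 | items 5–9: 5 |
| Secondary | 5 | items 10–12: 3 |
| Total | 11 | 12 |
| AEs counted | treatment-related | no limit stated |
| AE period | to study completion | insertion, use, removal |
| Readmissions counted | device-related | no limit stated |
| Prescribed feeding | absent | primary |
| Procedure time | secondary | absent (usability measure in 8.3) |

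**Precedence.** No statement in the protocol ranks one list above the other.

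**AE period.** The Section 8.2 wording stops at removal. Yet the synopsis safety assessment covers follow-up after removal, Section 11.3.1 collects AEs from enrolment through follow-up, and Section 11.1 anticipates post-removal obstruction, perforation and bleeding. The endpoint wording is therefore narrower than the collection.

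**Feeding period.** Table 3 places removal at day 90 and termination at day 120. Taken literally, 120 − 90 = 30 days of the study period fall after the device is out. The Tube Utilization Form runs from Visit 3 to Visit 6. Its content as described in Section 10.1.2 includes the method and ease of feeding, but not delivered against prescribed feeding. The case report form is not shown, so it may capture this elsewhere.

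**Can either safety count be derived?** For AEs, yes: Section 11.3.1 has causality assessed and Section 12 tabulates by relation. For readmissions, probably: inpatient hospitalization is an SAE (Section 11.3.3), reporting does not depend on relatedness (Section 11.3.4), and Section 12 tabulates by seriousness and relation.

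**Conditional illustration.** Section 9.2.4 anticipates that about 20% will die within the 4 months. With 15 treated, 0.20 × 15 = 3 expected deaths. Suppose exactly 3 occur, all are judged unrelated and fall before the end of removal, and no participant has any other AE. The AE endpoint is then:

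- synopsis: 0/15 = 0% (exact 95% interval 0 to 21.8%)
- Section 8.2: 3/15 = 20% (4.3% to 48.1%)

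**Pre-existing conditions.** The sentence ties the denial of AE status to worsening. The evident intent is the opposite: a stable condition is not an AE and an unexpectedly worsened one is. Serious worsening is still reportable under Sections 11.3.3 and 11.3.4, which contain no exception for pre-existing disease. Non-serious worsening has no such second route.

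**The case against.** The best case for leaving the text alone is that little depends on it. The study has 15 patients and is descriptive, with no test or success threshold, and the events are collected under either list. Of the extra items in Section 8.2, concomitant medications and insertion-site examination are assessments without a metric that are collected anyway, and procedure time is recorded whatever its label. All of that stands, and it limits the point to wording. It does not say which count is the endpoint.

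Five stronger readings are tempting, and the protocol does not support them.

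- *Dislodgement also conflicts.* The synopsis has "Number of accidental dislodgements during study follow up until device removal at 3 months" and Section 8.2 has "To evaluate accidental dislodgement during study follow up". The device is out after Visit 6 and the form that records dislodgement ends there, so both wordings give the same count.
- *Post-removal events are lost.* Visit 7 asks about AEs and has its own safety form. Only the endpoint wording leaves the month out.
- *The safety counts cannot be recovered.* The reporting and tabulation rules should yield both versions.
- *Three deaths separate the two AE counts.* They do so only if unrelated and only if those patients have no related AE. Section 11.1 attributes 6.5% to 19% mortality by day 30 to complications, so unrelatedness cannot be presumed.
- *Section 11.3 removes all worsening.* In strict logic, *only if* makes worsening necessary for exclusion and not sufficient. The sentence is a drafting slip, and serious events are protected. What remains is that site staff work from the written rule and that, by Section 11.1, most patients have several comorbidities.

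**Conclusion.** The point holds as an internal inconsistency that should be corrected. The two lists differ on relatedness for AEs and readmissions, on the stated AE period, on a fifth primary performance endpoint and on the status of procedure time, and nothing ranks them. The size is 2 against 4 safety endpoints and 4 against 5 primary performance endpoints. No error rate, threshold or sample size changes. The harm is that the headline safety and primary results are not fixed before the data are seen. The contrast of 0/15 with 3/15 shows how far apart the AE results could be under its stated conditions; it is not a forecast, and replacement of early leavers (Section 9.2.4) could make the number treated exceed 15.

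The Section 11.3 sentence is a separate defect. If followed as worded, it could leave non-serious worsening of pre-existing conditions unrecorded, and no later tabulation by relation would restore it. Its frequency cannot be estimated from the protocol.

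**What to change.** - Put one endpoint list in both Section 3 and Section 8.2.
- Define the AE and readmission endpoints through Visit 7, and report the any-cause and the device-related count for each.
- Either take prescribed feeding off the primary list, or limit it to the time the device is in place (Visit 2 to Visit 6) and confirm that an existing form captures it.
- Give procedure time one status: secondary endpoint or usability measure.
- Reword Section 11.3 so that a pre-existing condition counts as an AE only when it becomes worse than its expected course.

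The cost is protocol wording and a check of the existing forms, with no added visits or patients. The reported AE count may be higher than the related-only count in the synopsis.

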#### Secondary:

- 10. To evaluate usability by Physician filling a user questionnaire.
- 11. To evaluate usability by the patient or caregiver during long term use filling a user questionnaire.

ficmedical	– Study Protocol –	Protocol No.: FM-01 Version 5.1 Page 24 of 55
Safety and Usability Evaluation of the Fidmi Low-Profile Enteral Feeding Device		CONFIDENTIAL

12. To be able to validate correct (color) selection of 'Measuring Cannula' by residual tube measurement [design endpoint]

#### 8.3 USIBILITY STUDY MEASURES

#### Placement

- 1. Procedure time length (from endoscope intubation to end of procedure).
- 2. Difficulty of the procedure in general compared to routine procedure [Time Frame: Intra-procedural] Scored by the endoscopist on a 10-point Visual Analogue Scale).
- 3. Endoscopic measurement clear, simple and decisiveness of color scale evaluation, accurate length estimation.
- 4. Need for additional needle puncture (sheath kink, loss of visualization).
- 5. Ease of device insertion through the esophagus [questioner].
- 6. Ease of tube exteriorization through abdominal wall [questioner].
- 7. Placement location in the gastric body (low (pre pyloric) mid, high).
- 8. External bumper connection Tactile feedback, confidence in secured connection [questioner].
- 9. Measurement and evaluation of the Residual Tube at the end of the procedure - ensure residual is not "over protruding".

#### Post placement utilization. [Time Frame: 3 months]

- 10. Patency of disposable tube (partial or clogged tubes).
- 11. Disposable tube performance (ease of replacement, jammed tube, leakage).
- 12. Patency of the affixed main tube which is defined as time period between device placement and need for re-intervention (e.g. - flushing).
- 13. Measurement and evaluation of the Residual Tube at follow up visits ensure residual is not "over protruding".
- 14. Patient discomfort during long term use (Granulation tissue at the insertion site, limitation, esthetic etc.)

#### Removal

- 15. Dismantling tactile feedback (Obvious, vague scale).
- 16. Force needed for bumper-less shaft extraction compared to standard skin level removal of collapsible bumper graded: similar harder, lighter, much lighter, negligible (comparable to endoscope withdraw from esophagus.
- 17. Patient discomfort during the procedure.

#### **Bumper flanges expulsion**

18. Sensation in communicating patients.

fic medical	– Study Protocol –	Protocol No.: FM-01 Version 5.1 Page 25 of 55
Safety and Usability Evaluation Enteral Feeding Device	of the Fidmi Low-Profile	CONFIDENTIAL

19. Complete expulsion fluoroscopically proven by abdominal X-Ray imaging (in case particle/s from the bumper can be seen in the imaging a further follow visit will be scheduled only in case of symptoms related event/s, as per physician discretion)

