#### 10.1.2 PATIENT FOLLOW UPS AND PEG REMOVAL

Patients will be monitored for follow-up after 2, 30, 60 and 90 and 120 days following their PEG insertion/replacement procedure and will be evaluated by the study nurse for their medical conditions. PEG device removal will be conducted 3 months following its placement.

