#### Visit 6: Follow up after 3 months +/- 10 and Fidmi device removal/replacement by balloon gastrostomy.

Prior to the procedure the patient will be asked to report his nutritional status (malnutrition defined as a body mass index [BMI] <19 kg/m^2) and any stomal complication (wound infection, peristomal leakage, hypergranulation, pressure ulcer, any skin lesion adjacent to external bumper) – all will be investigated by the study nurse using Visit 6 safety Follow Up Form. In addition patient will be asked regarding his postoperative morbidity, any other Adverse Events, Concomitant medications.

Illuminated clear photos of the insertion site will be taken:

- Frontal to the insertion site/ external bumper
- Perpendicular (from the profile) to the insertion site/ external bumper
- In close perspective if outstanding issues (medical or technical) are observed

Study nurse will also investigate tube performance: accidental dislodgement, buried bumper, gastric outlet obstruction, tube leakage, Residual Tube above skin evaluation, number of scheduled tube replacement, method of feeding (bolus, continues gravity, mechanical pump etc.), Scale 1-10 – ease of connecting the extension tube, ease of feeding, any replacements of disposable tubes other than scheduled (and reason) using Visit 6 Tube Utilization Form

ficmedical	– Study Protocol –	Protocol No.: FM-01 Version 5.1 Page 36 of 55
Safety and Usability Evaluation of the Fidmi Low-Profile Enteral Feeding Device		CONFIDENTIAL

The following assessments will be conducted prior to device removal/ replacement by balloon gastrostomy:

- a) Physical examination
- b) Vital signs

\*An endoscopic examination is not required but may be performed on a need base, and following the investigator discretion.

In case a Gastrostom replacement is required, the study investigator will advise the patient from various types of technologically equivalent or similar devices including 'low profile' types. The replacement procedure will be performed routinely as specified in the Instruction for Use.

The following assessments will be conducted following the device removal/ replacement by balloon gastrostomy:

c) PEG Physician usability Form

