#### Study PEG removal Form:

Procedure duration, heart rate at the end of the operation, amount and type of analgesia consumed, postoperative bleeding, use of anti-bleeding agents (such as tranexemic acid (hexakapron)).

Endoscopist feedback Form: Endoscopist 10-point Visual Analogue Scale for removal procedure difficulty.

- d) Patient PEG removal/ replacement Feedback Form
- e) Study Patient Discharge form.

The discharging study investigator will instruct the patient (or his care giver) to immediately call the site in case of: vomiting, swollen belly, repeated abdominal aches and general deterioration (for demented patients). In case there is a suspicious of GI perforation or hemorrhage bowel obstruction the study investigator will schedule an un-scheduled visit.

C medical	– Study Protocol –	Protocol No.: FM-01 Version 5.1
		Page 37 of 55
Safety and Usability Evaluation of the Fidmi Low-Profile		CONFIDENTIAL
Enteral Feeding Device		

The patient will be asked for his most convenient day for the termination visit (Visit 7 study termination, see below) - this day will be recorded by the study nurse at the Patient Visits Log.

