## Visit 7: Follow up after 4 months +/- 10, X-ray and termination visit

In compliance with the Centric Patient Approach, a home X-ray examination will be offered to the patient and his family. If chosen, a certified technician (Medix at Home, FDA and MOH approved) will visit the patient facility at the specific day scheduled together, in order to conveniently perform abdominal X-ray examination (required to verify Bumper flanges expulsion). A copy of the imaging will be provided to delegated sub-investigator for evaluation.

Following the X-ray examination, a delegated study member will call the patient facility to verify no technical issues occurred. The patient will be asked to report his nutritional status (malnutrition defined as a body mass index [BMI] <19 kg/m^2) and any stomal complication (wound infection, peristomal leakage, hypergranulation, pressure ulcer, any skin lesion adjacent to external bumper) – all will be investigated by the study nurse using Visit 7 safety Follow Up Form. In addition, patient will be asked regarding his postoperative morbidity, any other Adverse Events and Concomitant medications.

Alternatively, the patient will be admitted to the Gastrology Institute at Shaare Zedek Medical Center, Jerusalem an hour before the planned X-ray examination scheduled time accompanied by the study nurse. Prior to the examination he will be asked to report his nutritional status (malnutrition defined as a body mass index [BMI] <19 kg/m^2 and any stomal complication (wound infection, peristomal leakage, hypergranulation, pressure ulcer, any skin lesion adjacent to external bumper) – all will be investigated by the study nurse using Visit 7 safety Follow Up Form. In addition,

ficmedical	– Study Protocol –	Protocol No.: FM-01 Version 5.1 Page 38 of 55
Safety and Usability Evaluation of the Fidmi Low-Profile Enteral Feeding Device		CONFIDENTIAL

patient will be asked regarding his postoperative morbidity, any other Adverse Events, Concomitant medications.

The following forms will be completed:

- a) Post PEG removal imaging Form
- b) Termination visit

\*An endoscopic examination is not required but may be performed on a need base, and following the investigator discretion.

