#### Table 3 - Visit procedure chart

	Enroll and d place	evice		Follow	/ Up Per	iod	
Procedure	Screening & Enrollment	Fidmi device insertion	Sub-I visit in patient facility	Sub-I visit in patient facility	Follow up call with the patient	Fidmi device removal	X-ray and termination visit
Visits	V1	V2	V3	V4	V5	V6	V7
Time Schedule (Days)	-7	0	2	30	60	90	120
Time Window (+/- Days)	7		1	10	10	10	14
Informed consent	Х						
Demographics+ Med. history	Х						
Concomitant medications	Х	х					
Physical exam	Х	x	х	х		х	
Vital signs	Х	x	х	х		х	
Adverse event evaluation		x					
Endoscopy recording		x					
Photos of the insertion site		x	х	х		х	
PEG usability Form (physician)		х				х	
Patient Discharge form		х				х	
Safety Follow Up Form			Х	Х	Х	х	x
Tube Utilization Form (patient/care giver)			х	х	х	x	
Patient feedback Form						х	
Patient Bumper flanges							
expulsion Form							х
X-ray imaging (home/clinic)							х
Post PEG removal imaging Form							х
Termination Visit							х
Subject Visit log		Х	Х	Х	Х	х	
Un-scheduled visit Form (if needed)							

F medical	– Study Protocol –	Protocol No.: FM-01 Version 5.1 Page 40 of 55
Safety and Usability Evaluation	of the Fidmi Low-Profile	
Enteral Feeding Device		CONFIDENTIAL

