### **11 SAFETY ASSESSMENT**

#### 11.1 Anticipated Adverse Events

Placement complication: excessive stoma wound bleeding, over tightened external bumper, gastric and/or esophageal laceration, aspiration, device unintended disassembly, need for more than one needle puncture

Post placement complication; [Time Frame: 1week-4 months]: Fever, gastric distention, infection, blockage/ occlusion, tissue necrosis, migration, erosion/embedding into the gastric wall ("Buried Bumper Syndrome"), aspiration, bleeding, fistula, GE reflux, pain, perforation, ulceration, pressure sores, skin lesion (tissue granulation) adjacent to external bumper, dumping syndrome, tube clogging, malposition, leakage, kinking, inadvertent removal, small bowel obstruction, and granulation tissue.

Post removal complication: Bowel obstruction, Bowel peroration, GI bleeding, painful defecation.

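### Sensation as the bumper pieces pass is solicited only once, at Visit 7, up to 50 days after removal (54 by Table 3), on a form the Visit 7 list omits, so mild symptoms may be missed

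*Protocol*

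**What the plan says.** Section 8.3 has two measures under bumper flange expulsion. Item 18 is "Sensation in communicating patients", with no time point or scale. Item 19 is X-ray confirmation that the pieces have gone.

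Table 3 has a row for a patient form on expulsion (the row label begins "Patient Bumper flanges"), with one tick, in the Visit 7 column. In section 10.1.2, the Visit 7 text says "The following forms will be completed" and then lists two items, the post-removal imaging form and the termination visit. The same text separately calls for the Visit 7 safety follow-up form. The expulsion form is not mentioned anywhere in section 10.1.2.

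At Visit 6 the patient or caregiver is told to "immediately call the site in case of: vomiting, swollen belly, repeated abdominal aches and general deterioration (for demented patients". Section 11.1 gives the expected events after removal as "Post removal complication: Bowel obstruction, Bowel peroration, GI bleeding, painful defecation", and the synopsis lists the same four. Painful defecation is therefore an anticipated complication that the call-in list does not name.

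Contacts are set "after 2, 30, 60 and 90 and 120 days following their PEG insertion/replacement procedure". Removal is at day 90 and the next scheduled contact is at day 120.

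**The concern.** The device's bumper is broken into pieces that leave through the bowel (section 5.3), and dismantling and removal are part of the study objective (section 7.1). How the pieces pass is therefore something this first-in-human study should describe well. Passage is a short event at an unknown time after Visit 6, yet the one enquiry directed at it is a retrospective form at Visit 7. The population includes patients with dementia who enter through a guardian, and item 18 is restricted to those who can communicate.

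Forgotten or unreported mild symptoms can only lower the count, so any error of this kind favours the device. With 15 patients and purely descriptive reporting, one or two lost reports would change what the results table says. Item 18 is not itself a listed endpoint. Painful defecation is, however, a named complication, and where it is treatment-related it belongs in the synopsis's first safety endpoint.

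**Working it through.** The protocol states no interval from removal to Visit 7 and no sample size calculation, so there is no figure of its own to reproduce. Two checks apply.

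**1. Gap between removal and the enquiry**

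Inputs:
- Visit 6: "Follow up after 3 months +/- 10 and Fidmi device removal/replacement by balloon gastrostomy", that is day 90 ± 10, or days 80 to 100.
- Visit 7, visit text: "Follow up after 4 months +/- 10, X-ray and termination visit", that is day 120 ± 10, or days 110 to 130.
- Visit 7, Table 3: day 120 ± 14, or days 106 to 134. The 14-day tolerance on study duration in section 7.3 agrees with Table 3 and not with the visit text.

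Formulas: shortest gap = earliest Visit 7 − latest Visit 6; longest gap = latest Visit 7 − earliest Visit 6.

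| Visit 7 window | Shortest | Nominal | Longest |
|---|---|---|---|
| Visit text, ± 10 | 110 − 100 = 10 days | 120 − 90 = 30 days | 130 − 80 = 50 days |
| Table 3, ± 14 | 106 − 100 = 6 days | 120 − 90 = 30 days | 134 − 80 = 54 days |

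Recall time = gap − days from removal to passage. The protocol gives no passage time, so the gap is an upper bound on recall time.

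**2. Routes by which a passage symptom could reach the record**

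| Route | Where | What it gives |
|---|---|---|
| Expulsion form | Table 3, Visit 7 only | The only form named for expulsion from the patient's side; retrospective; absent from the Visit 7 form list |
| Call-in instruction | 10.1.2, Visit 6 | Started by patient or caregiver; abdominal aches are named, painful defecation is not |
| Adverse events collected throughout | 11.3 | Between Visits 6 and 7 there is no scheduled contact, so it depends on a call |
| Safety form and general question | 10.1.2, Visit 7 | Specific prompts are nutrition and stoma; anything else falls under a general question, asked in retrospect |
| X-ray | 8.3 item 19; Visit 7 | Whether pieces remain, not how they passed |

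No route in the table asks about passage while it is happening. The one that asks about it specifically appears in Table 3 but not in the Visit 7 form list.

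No expected number of missed events can be calculated. That would need the rate of painful passage, the passage time and the share of events recalled, and the protocol gives none of them.

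**The case against.** The strongest reply is that several other channels exist. Painful defecation is an anticipated event, adverse events are collected from enrolment through follow-up, and section 11.2 provides a 24-hour emergency call. At Visit 6 patients and caregivers are told to call for repeated abdominal aches, and Visit 7 asks about any other adverse event. All of this stands, and severe or persistent symptoms would very probably be caught. What remains exposed is the mild or brief symptom that prompts no call.

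A reader might infer that painful passage is under-counted as a matter of fact. The documents do not support that, because they give no event rate, passage time or recall loss. It is a risk with a known direction and an unknown size. The 50- and 54-day extremes also need removal at the early edge of its window and Visit 7 at the late edge of its own; the nominal gap is 30 days.

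A reader might also infer that this form is the only patient-level information on expulsion, or that patients who cannot communicate contribute nothing. Neither holds. The X-ray is planned for every patient who reaches Visit 7, adverse events are recorded for each patient, and caregivers are included in the call-in instruction, which names general deterioration in demented patients.

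It can fairly be said that the form mismatch is editorial, since section 10 refers the reader to Table 3 for the schedule, and Table 3 does contain the form. That lowers its weight, but staff working from the visit text would still not see it. The Visit 7 tick might mark collection of a form issued earlier; the protocol does not say so. Lastly, item 18 is one of 19 usability measures in a descriptive study of 15 patients, so this is an inexpensive improvement and not a threat to the study's validity.

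**Conclusion.** The point holds as a weakness in data collection, together with an inconsistency in the current text. Expulsion sensation is specifically solicited once, in retrospect, 10 to 50 days after removal by the visit text or 6 to 54 days by Table 3; both ranges are upper bounds on recall time. The form for it is in Table 3 but not in the Visit 7 form list, and the call-in list does not name an anticipated post-removal complication. Mild or transient passage symptoms may be missed, in the device's favour.

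This rests on the visit windows as printed, on there being no scheduled contact between Visits 6 and 7, and on the Table 3 tick meaning that the form is completed at Visit 7. It does not rest on any assumed recall rate, and no size can be given for the possible loss.

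**What to change.** - Issue the Patient Bumper flanges expulsion Form at Visit 6, to be filled in at home as events occur, for example with date, whether a piece was seen, pain and blood. Move or add the Table 3 tick to show issue at Visit 6 and collection at Visit 7.
- For patients who cannot communicate, let the caregiver record the observable items. Table 3 already has patients or caregivers completing the tube utilization form.
- Collect the form at Visit 7. In the home X-ray route, have it read out during the follow-up call.
- Add the form to the Visit 7 list in section 10.1.2 so that it agrees with Table 3, and reconcile the two Visit 7 windows (10 and 14 days) at the same time.

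The cost is one line in section 10.1.2, a change to one Table 3 row, and a small burden on the patient or caregiver. The form's content is not shown in the protocol, so it may need minor adaptation for home and caregiver use. No visit, test or clinical rule is added.
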